5.3 Safety Evaluation

Safety will be monitored by adverse events reporting. The frequencies of AEs by type, body system, severity and relationship to study supplement will be summarized. SAEs (if any) will be described in detail.

6 STATISTICAL CONSIDERATIONS

6.1 Primary Endpoint

The primary aim is to utilize the MBT, CFA and BC methods to characterize the fat and energy absorption patterns to compare fat and energy absorption from the diet in subjects with CP and healthy subjects. We will also determine if fat and energy absorption will improve after pancreatic enzyme medication administration in subjects with CP utilizing the MBT, CFA and BC methods to characterize the fat and energy absorption patterns.

6.2 Secondary Endpoint

The secondary aim is to utilize the data from the MBT, CFA and BC outcomes to optimize the MBT design and application by reducing the time and blood samples required. We will also explore the utility of the MBT compared to the CFA and BC (both require the burdensome 72-hour total stool and dietary intake collection) in identifying differences in fat absorption between subjects with CP and healthy individuals and within the CP cohort, with and without pancreatic enzyme medication. We will also explore the association of specific genotypes with fat malabsorption in the context of CP.

6.3 Statistical Methods

Analysis will begin with descriptive analyses of the study sample using means, standard deviations, medians, and ranges for continuous variables, and frequency distributions for categorical variables. Descriptive statistics and exploratory graphing such as frequencies, means, standard deviations, box plots, and scatter plots will be used to assess the normality of the data in terms of the presence of skew and/or outliers.

6.3.1 Efficacy Analysis

Statistical Analysis: H1 and H2: Descriptive statistics for MBT, CFA% and BC outcomes (mean, standard deviation, median, range, 95% CI) will be calculated for the CP cohort and for the healthy comparison group, and differences between CP and healthy groups assessed with unpaired t tests. For the MBT outcomes, a moment-based pharmacokinetic (PK) analysis will be performed based on non-compartmental methodology using WinNonLin version 9.1 (Pharsight, Cary, NC). Baseline (C_0) and maximum (C_{max}) plasma concentrations are calculated, and area under the curve from time zero to eight hours (AUC) is calculated using the linear trapezoid method. PK parameters can then be compared between treatment groups using a paired t-test or Wilcoxon signed rank test as appropriate. To describe HA exposure relative to that of PA, the ratio of the HA to PA C_{max} (C_{max} HA/PA) and AUC (AUC HA/PA) is calculated for each subject after molar transformation and dose-normalization of exposure metrics⁴⁹. Alternately, population PK analyses for repeated-measures endpoints can be conducted via nonlinear mixed-effects modeling with a qualified installation of the nonlinear mixed-effects modeling (NONMEM) software, Version VII, Level 2.0 (ICON

Development Solutions, Hanover, MD)⁴⁸. Using this method, population PK modeling is conducted by simultaneously fitting structural PK models to both PA and HA concentrations⁵⁰.

Descriptive statistics for MBT, CFA% and BC outcomes (mean, standard deviation, median, range, 95% CI) will also be calculated for the CP cohort with and without pancreatic enzyme medication administration, and the significance of changes over time assessed with paired t tests. HA and PA concentrations will be transformed to molar quantities and the ratios for HA to PA C_{max} and AUC and the associated 95% confidence interval will be calculated. A mixed effects modeling approach will be employed to examine the correlation of subject characteristics (age, BMI, sex, disease status, etc.) to PA and HA exposure metrics derived from the non-compartmental analysis to assess change over time in MBT response to pancreatic enzyme medication administration in subjects with CP. Metrics to be tested will be CFA%, PA and HA C_{max} , AUC, HA/PA C_{max} and AUC ratio and the %HA response compared to the healthy reference group. A value of $p < 0.05$ will be considered statistically significant.

H3: Pharmacokinetic modelling will be employed to identify the three to four blood samples over the first four to five hours of the MBT that provide the best and most reproducible estimate of the full eight-hour MBT (nine blood samples) in the CP cohort and healthy comparisons. The goal is a shorter sampling scheme for the MBT to optimize its use as a clinical diagnostic test.

In exploratory analyses, we will compare the estimates of percent fat absorption from the MBT with both the CFA% from the 72-hour fecal fat and diet analysis and the BC results (energy loss in the stool). We will compare the methods for detection of fat malabsorption as measured by CFA% and BC with fat absorption as measured by MBT for the subjects with CP compared to healthy individuals and also within the CP cohort before and after pancreatic enzyme medication use. A correlation analysis will be conducted to evaluate the performance of the MBT relative to that of the CFA%. HA and PA C_{max} , AUC, and HA/PA ratios will be plotted against CFA% or BC caloric loss to explore the relationship between the two tests. Any relationships observed in the plots will be further explored using correlation analysis and appropriate regression analysis as dictated by the observations. If a reasonable model can be developed to describe the response of MBT, CFA% and BC response to pancreatic enzyme medication treatment within the CP cohort, additional simulation studies will be performed to further examine the performance characteristics of both tests.

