1.5 Relevant Literature

CP is a disease of chronic pancreatic inflammation that is progressive with scarring and irreversible tissue damage resulting in loss of endocrine and exocrine function. Patients often have chronic abdominal and back pain, nausea and vomiting, weight loss, steatorrhea and increased number of bowel movements as the disease progresses. Diabetes may occur later in the course. Symptom severity is described as mild, moderate or severe and can change over time in individuals. Incidence is estimated to be from about 4.4 to 11.9 per 100,000 people per year⁷⁻¹⁴ and is more common in men. The prevalence of CP is estimated to be from about 37 to 42 per 100,000 people^{9, 11}. The approach to diagnostic testing and clinical care is not standardized, in part because there is no standard approach to diagnosis, diagnostic criteria vary, and many diagnostic approaches are costly and invasive⁴. Related to this protocol, there is little information on nutrition status and disease outcomes, and no clinical standards for screening or treatment of nutrition-related complications of CP. This proposal focuses on the specific issue of progressive loss of exocrine pancreatic function to the point of clinically meaningful malabsorption of dietary fat, and

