3 INVESTIGATIONAL PLAN

3.1 General Schema of Study Design

3.1.1 Screening Phase

Potential subjects will be screened using the protocol inclusion and exclusion criteria. Subjects will be recruited from regional academic hospitals and gastroenterology, and pancreatology subspecialty centers. Primary recruitment centers will include: 1) University of Pennsylvania Medical Center Hospital; 2) Pennsylvania Hospital; 3) Presbyterian Hospital; and 4) Philadelphia Veterans Administration Medical Center. Other likely collaborators and recruitment centers may include: 1) GI Centers at the Jefferson Medical Center; 2) Main Line Medical Center (Lankenau and Bryn Mawr Hospitals); and 3) other regional centers. These outside institutions will be involved with recruitment of subjects only and will otherwise not be engaged in the research. We will recruit the healthy subjects from the greater Philadelphia region using general adult practices, flyers, and recommendations from subjects with CP regarding healthy family and friends interested in participating. The CHOP Recruitment Enhancement Core (REC) will be utilized to recruit healthy adult subjects. The Recruitment Enhancement Core provides assistance with recruitment plan development and may assist in identifying and contacting potential participants using the Clinical Recruiting Unit (CRU), the CHOP Recruitment Registry and internal communication resources. Our research team anticipates no difficulty in enrolling well-qualified participants with the proposed sample size and staff (see **Table 2. Study Timeline**). Informed consent will be obtained prior to any study related procedures being performed, and this will include the discontinuation of pancreatic enzyme medication for those participants who are taking this medication at the time of enrollment in the study.

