3.4 Study Population

3.4.1 Inclusion Criteria

Chronic Pancreatitis Cohort

- Chronic pancreatitis diagnosis by gastroenterologist. Participants with CP will be characterized based on the TIGAR-O (toxic, genetic, autoimmune, recurrent, obstructive) etiology system, on pancreatic morphology (Cambridge criteria) when available, and on physiological state (exocrine and endocrine function) as recommended by the recent American Pancreatic Association Practice Guidelines⁴.
- Age 30-75 years old
- Evidence of at-risk for malabsorption including: 1) history of use of and response to pancreatic enzyme medication; 2) history of unintentional weight loss; 3) history of increased stools per week or fatty stools; and/or 4) other clinical signs or symptoms suggestive of fat malabsorption
- In usual state of health for past two weeks including no change in medications

-
- Able to consume a moderate fat diet for stool evaluations
 - Able to participate in the study for about four weeks with two study visits

Healthy Cohort

- Age 30-70 years old
- No known chronic disease that would affect dietary intake or fat absorption
- In usual state of health for past two weeks, with stable medications, diet and weight
- BMI from 14-35
- Able to consume a moderate fat diet for stool evaluations
- Able to participate in the study for about one week with one study visit

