3.4.2 Exclusion Criteria**Chronic Pancreatitis Cohort**

- Evidence of normal fat absorption in medical record
- Medications that alter fat absorption (i.e. orlistat, other weight loss medications, ursodeoxycholic acid)
- Allergy to pork products
- History of intestinal blockage or fibrosing colonopathy
- Current diagnosis of gout and treatment with allopurinol medical therapy
- Pregnancy or breast feeding

Healthy Cohort

- Evidence of fat malabsorption
- Medications that alter fat absorption (i.e. orlistat, other weight loss medications, ursodeoxycholic acid)
- Pregnancy or breast feeding

4 STUDY PROCEDURES**4.1 Screening**

Subjects will be screened with support from the clinical sites using the protocol inclusion and exclusion criteria. Clinic staff will inform eligible individuals of the existence of this study and ask for permission from these individuals to share their contact information with the CHOP study staff. Either verbal or in person screening can occur. In the instance of screening over the phone, verbal subject permission will be obtained. In the instance of in person screening, study staff will obtain a signature from the subject. For both instances, screening consent will occur prior to obtaining any information from study subjects.

All subjects will be enrolled in their usual state of good health defined as no hospitalizations, emergency room or unscheduled acute illness clinic visits, and with activity levels and food intake considered typical by the subject for two weeks prior to Visit 1.

Healthy subjects will be identified from the greater Philadelphia region using referrals of friends and family of the subjects with CP. The subjects with CP will first ask for potential healthy subjects'

permission to release their contact information to the CHOP study team. Healthy subjects will also be identified using general adult practices, CHOP staff interested in participating in a research study, and through the CHOP Recruitment Enhancement Core (REC). The Recruitment Enhancement Core provides assistance with recruitment plan development and may assist in identifying and contacting potential participants using the Clinical Recruiting Unit (CRU), the CHOP Recruitment Registry and internal communication resources. Verbal subject permission will be obtained prior to obtaining any health information from these subjects to determine eligibility.

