For the CFA% outcome, our experience has been in CF and PI, with average CFA% of $81 \pm 14\%$ in one study⁶⁷ and $83 \pm 10\%$ in another⁷¹ when subjects were on pancreatic enzyme medication. In comparison, in healthy subjects, CFA% is typically $\geq 93\%$. From the literature for CP, a number of clinical trials have used CFA% to describe fat malabsorption in subjects with CP and confirmed pancreatic insufficiency before and after administration of pancreatic enzyme medication. Ramesh et al¹⁵ found an increase in CFA% from 66.7 ± 14.0 before pancreatic enzyme medication to $88.9 \pm 5.2\%$ after pancreatic enzyme medication (change of $22.7 \pm 12.2\%$) in adults with CP from India. Also in adults from India participating in a placebo-controlled trial, Thorat et al¹⁶ saw CFA% increase from 66.5 ± 14.1 to $86.1 \pm 7.5\%$ in those taking pancreatic enzyme medication compared to an increase from 67.0 ± 14.0 to $72.9 \pm 11.5\%$ for placebo, a treatment effect of 13.7% (95% CI: 9.1, 18.2) after one week of pancreatic enzyme medication. From this combined experience with variability of the CFA% in both CF and CP, 21 subjects in each group will have 80% power to detect a difference in means of 10% (the difference in CFA% between health group mean of 95% and CP group mean of 85%) assuming that the common SD is 11% using a t-test with $\alpha = 0.05$.

For the BC method, there is limited information for typical variability in calories lost in stool in either healthy subjects or those with malabsorption diagnoses. Using 72-hour stool assessments, Wierdsma et al⁷⁰ has recently reported average daily energy loss of 213 ± 66 kcal in 23 healthy adults. This loss was less in those >50 years old (197 ± 49 kcal). If we assume that approximately 200 kcal/day are lost in the stool of healthy subjects, 21 subjects in each group will have 80% power to detect a difference in means of 50 kcal (the difference in BC between health group mean of 200 and CP group mean of 250 kcal lost in stool) assuming that the common SD is 56 using a t-test with $\alpha = 0.05$.

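### H1 compares unmatched CP and healthy groups by unadjusted t test only; no age- and sex-adjusted difference is pre-specified

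*Combined protocol and SAP*

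**What the plan says.** H1 is a primary hypothesis: untreated CP subjects are expected to absorb less fat and energy than healthy subjects on MBT, CFA and BC. Section 6.3.1 (Efficacy Analysis) plans descriptive statistics by cohort, with "differences between CP and healthy groups assessed with unpaired t tests". The synopsis says the same. Neither place lists a covariate.

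Age, BMI, sex and disease status appear once in the analysis plan, in a mixed-effects model of PA and HA exposure. Its stated purpose is "to assess change over time in MBT response to pancreatic enzyme medication administration in subjects with CP", which is H2. BC is not among the metrics listed with it.

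Sections 3.2 and 9.1 state that the study is not randomised. In section 3.4.1 the healthy cohort is "Age 30-70 years old", while CP subjects may be up to 75. Section 3.1.1 recruits healthy subjects "using general adult practices, flyers, and recommendations from subjects with CP regarding healthy family and friends interested in participating", together with the hospital's recruitment core; section 4.1 adds "CHOP staff interested in participating in a research study". No age or sex quota is given.

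Two background statements bear on comparability. Section 1.5 says that CP "is more common in men". Section 6.4 cites "average daily energy loss of 213 ± 66 kcal in 23 healthy adults" and adds "This loss was less in those >50 years old", with a value of 197 ± 49 kcal in that older subgroup.

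**The concern.** CP subjects come through specialty centres and healthy subjects through general channels, so similar age and sex distributions would be a matter of luck. If either variable is related to an outcome, the unadjusted difference mixes that relation with the effect of CP. The direction is not fixed. For BC, an older CP group would pull the difference toward zero, and a younger one would inflate it.

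The difference itself matters as well as the p-value, because the healthy cohort is there to supply comparison data for interpreting the three tests. If adjustment is decided only after an imbalance is seen, the choice of covariates is open to the charge of selection.

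**Working it through.** **1. The plan's own figures.** Two-sample t test, two-sided alpha 0.05, noncentral t, using the differences and SDs in section 6.4:

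| Outcome | Difference / SD | Effect (SD) | Stated n per group | Power at stated n | Power at 22 |
|---|---|---|---|---|---|
| MBT HA/PA | 0.60 / 0.68 | 0.88 | 22 | 81.6% | 81.6% |
| CFA% | 10 / 11 | 0.91 | 21 | 82.0% | 83.8% |
| BC | 50 / 56 | 0.89 | 21 | 80.6% | 82.5% |

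The stated sizes reproduce. They rest on the unadjusted test.

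**2. Age gap implied for BC.** Inputs are the overall 213 (SD 66, 23 adults) and 197 (SD 49) above age 50. The share over 50, f, is not given and is assumed.

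- Gap (younger minus older) = (213 − 197f)/(1 − f) − 197. At f = 0.5: (213 − 98.5)/0.5 − 197 = 229 − 197 = 32 kcal.
- The SD of the younger group is back-calculated from the total SD. SE = √(49²/n_old + SD_young²/n_young). At f = 0.5: √(49²/11.5 + 78.5²/11.5) = 27.3. The 95% CI uses 21 df.

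| Share over 50 | Gap (kcal/day) | SE | 95% CI |
|---|---|---|---|
| 30% | 23 | 26 | −31 to 77 |
| 50% | 32 | 27 | −25 to 89 |
| 70% | 53 | 36 | −21 to 128 |

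All three intervals include zero.

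**3. Effect on the unadjusted BC test.** Bias = imbalance × gap. With an excess of over-50s in CP, power is computed at a difference of 50 − bias, SD 56, 22 per group. With the reverse imbalance and no true difference, the false-positive rate is computed at a difference equal to the bias. The imbalances are assumptions.

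| Gap | Imbalance | Bias (kcal) | Power | False-positive rate (reverse imbalance) |
|---|---|---|---|---|
| 23 | 10 points | 2.3 | 79% | 5.2% |
| 23 | 30 points | 6.9 | 70% | 6.8% |
| 32 | 10 points | 3.2 | 77% | 5.4% |
| 32 | 30 points | 9.6 | 65% | 8.6% |
| 53 | 10 points | 5.3 | 73% | 6.1% |
| 53 | 30 points | 16.0 | 50% | 15.3% |

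**4. The age limits alone.** If ages were uniform within each range (assumption), the shares over 50 would be 25/45 = 55.6% and 20/40 = 50%, a 5.6-point difference. Bias = 0.056 × 32 ≈ 1.8 kcal, and power is 80%.

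**5. What adjustment costs.** The model has group, age (two classes here) and sex, so 44 − 4 = 40 df. With shares centred on 50%, variance inflation is 1/(1 − imbalance²): 1.01, 1.10 and 1.33 at 10, 30 and 50 points. Power if age explains none of the outcome:

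| Imbalance | BC | MBT | CFA% |
|---|---|---|---|
| 10 points | 82% | 81% | 83% |
| 30 points | 79% | 78% | 80% |
| 50 points | 71% | 70% | 72% |

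A simulation of BC (20,000 runs, random age class and sex, total SD 56) also allows for chance imbalance. With a true gap of 32, unadjusted versus adjusted power is 77% versus 83% at 10 points and 66% versus 80% at 30 points. With no gap, adjusted power is 81% and 76%. The adjusted false-positive rate is 4.9-5.1%.

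**The case against.** The strongest reply is that no harm has been demonstrated. The only documented asymmetry is the age limit; it is worth about 2 kcal and, if it makes CP older, works against H1. The false-positive figures need a younger CP group, which nothing in the documents suggests. The 10- and 30-point imbalances are assumed. The age effect is documented for one outcome, with an interval that includes zero, and Table 1 lists BC as secondary although section 5.2.2 calls it a primary outcome. No age effect on MBT or CFA% and no sex effect on any outcome is reported. The HA/PA ratio compares two fatty acids given to the same person, and CFA% is relative to recorded intake, so confounding may be less plausible there. The study is exploratory, and planned effects are near 0.9 SD.

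All of this stands, and it limits the weight of the point; it does not fill the gap. A further reply, that the mixed-effects model already covers age, sex and disease status, fails. Healthy subjects have one visit and no enzyme, so they have no change over time to contribute. The population PK option is not tied to the H1 contrast and has no stated covariates. The descriptive statistics in section 6.3 could at most reveal an imbalance, not its effect on the H1 difference.

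**Conclusion.** The concern holds, as a low-priority improvement. No adjusted H1 estimate is defined anywhere in the documents, so an age or sex imbalance could bias the primary between-group difference without any planned analysis showing it. How large the bias would be cannot be established from the documents. For BC it could range from negligible to 16 of the planned 50 kcal in the cases shown, depending on an assumed share over 50 in the cited sample and an assumed imbalance. For MBT and CFA%, and for sex, the concern is one of principle. H2 and the sample-size arithmetic are not in question.

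**What to change.** In section 6.3.1, keep the unpaired t test as the H1 test. Add, for each H1 outcome (MBT, CFA%, BC), a linear model with group, age and sex, reporting the adjusted CP-healthy difference with its 95% CI beside the unadjusted one. For MBT, name the metrics; the C_max and AUC HA/PA ratios used in section 6.4 are the natural choice. Tabulate age and sex by group. Leave BMI out of the model, because low BMI can be a consequence of malabsorption. State that the model assumes the same age slope in both groups, and check this by plotting each outcome against age by group.

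The change needs wording only, with no extra subjects. Exact age is computed in the database (section 9.2). Sex is on the abstraction list in section 5.1.1, and for healthy subjects it is implied by the pregnancy test at Visit 1; the SAP could say outright that it is recorded for both cohorts. The statistical price is two degrees of freedom plus the variance inflation shown above: small at modest imbalance, and down to 70-72% power at 50 points if age explains nothing. Aligning the age limits or frequency-matching healthy recruits is optional and not needed for this fix.

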The MBT uses the general approach of the commonly utilized glucose tolerance test, with consumption of a beverage containing the nutrient of interest (fatty acid, rather than glucose) followed by the determination of the timing and amount of the fatty acids in blood samples. The MBT consists of administering two odd-chain length fatty acids: pentadecanoic acid (PA), a free fatty acid that does not require pancreatic lipase for absorption; and triheptadecanoic acid (THA), a triglyceride that requires pancreatic lipase for hydrolysis to three heptadecanoic (HA) fatty acids. These two fatty acids were selected for the MBT for the following reasons: 1) they are found in small amounts only in dairy foods; 2) the vast majority of individuals have very low serum concentrations of PA and HA; 3) they are safe even in larger doses than typically found in the diet; and 4) they are easily identified in the serum by well-established laboratory methods and absorption pharmacokinetics that can be readily described. Following the ingestion of the MBT fatty acids, the pharmacokinetics of the fat absorption for both PA and HA is assessed over an 8-hour period and the relative absorption of HA/PA is determined. A moment-based pharmacokinetic (PK) analysis is performed based on non-compartmental methodology using WinNonLin version 9.1 (Pharsight, Cary, NC). Baseline (C_0) and maximum (C_{max}) plasma concentrations are calculated, and area under the curve from time zero to eight hours (AUC) is calculated using the linear trapezoid

method. PK parameters are then compared between treatment groups using a paired t-test or Wilcoxon signed rank test as appropriate. To describe HA exposure relative to that of PA, the ratio of the HA to PA C_{max} (C_{max} HA/PA) and AUC (AUC HA/PA) is calculated for each subject after molar transformation and dose-normalization of exposure metrics. Also, population PK analyses for repeated-measures endpoints is conducted via nonlinear mixed-effects modeling with a qualified installation of the nonlinear mixed-effects modeling (NONMEM) software, Version VII, Level 2.0 (ICON Development Solutions, Hanover, MD)⁴⁸. Using this method, population PK modeling is conducted by simultaneously fitting structural PK models to both PA and HA concentrations.

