5.2 Efficacy

5.2.2. Diagnostic tests, Scales, Measures

Malabsorption Blood Test (MBT): The **MBT primary outcomes** consist of parameters from pharmacokinetic analyses. The MBT consists of a simultaneous oral dose of pentadecanoic acid (PA), a free fatty acid, and triheptadecanoic acid (THA), a triglyceride with three heptadecanoic (HA) saturated fatty acids requiring hydrolysis by pancreatic lipase before HA can be intestinally absorbed (Patent # US 7402405 B2, July 22, 2008). The MBT with the PA and THA is delivered in a breakfast test meal after a 12-hour fast and 24 hours without dairy foods. Serum concentration

levels of PA and HA are assessed by gas-liquid chromatography (GC), from serum samples drawn prior to MBT and then hourly for eight hours. The MBT test meal is prepared immediately before consumption, with 5.0g of PA and 5.5g of THA blended into a test meal composed of 64g vanilla Scandishake (Axcan Scandipharm, Birmingham, AL), 6oz silk light chocolate soy milk, and 10ml microlipids (www.nestle-nutrition.com). The 8oz MBT test meal contains ~550 calories, 32 g fat, and 52% of calories from fat. The test meal was designed to be similar to a high fat dinner meal. Prior to administration of the MBT test meal, an indwelling catheter is placed for baseline (0 Hour) and subsequent blood draws at Hour 1, 2, 3, 4, 5, 6, 7 and 8 post ingestion for quantification of serum PA and HA. The MBT test meal is consumed within five minutes of the baseline blood draw. After the Hour 6 blood draw, subjects consume a 1000 kcal, low fat (12 g) lunch meal, and two blood samples will follow this meal (Hours 7 and 8). During the eight-hour protocol period, subjects are offered non-caloric and non-caffeinated beverages *ad libitum*. The 72-hour home stool collection will begin two days after the MBT visit, and the corresponding 3-day weighed food record will begin the day prior to the first day of the 72-hour stool collection.

Table 3. Protocol for each MBT visit

Protocol	Day 1	Day 2	Day 3	Day 4	Day 5	Day 6	Day 7	Day 8	Day 9
Enzyme-naïve: MBT #1 CP Healthy Comparisons	- Fast from 8pm - No dairy - No alcohol - Normal activity	- MBT at 8am - Lunch at 2pm - 9 hourly blood draws	Home Return to usual diet	- Diet record (day 1)	- Diet record (day 2) - 72-hour stool (day 1)	- Diet record (day 3) - 72-hour stool (day 2)	- 72-hour stool (day 3)		

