Plasma samples will be analyzed by a GC method at Wake Forest University (Winston-Salem, NC). Total lipids are extracted from 200 μ L of plasma following the method of Bligh and Dyer⁶⁶. Following methylation of the fatty acids in the total lipid extract, fatty acid methyl esters are extracted into iso-octane and 1 μ L was injected into the GC column for analysis using a Hewlett Packard 5890 series II gas chromatograph with a programmable cool on-column capillary inlet, flame ionization detector (FID), and HP7673 auto sampler/injector. Chromatographic data collection and analysis is via a serial connection to a computer running ChromPerfect Spirit™ chromatography data system (Justice Laboratory Software, Denville, NJ). The column used is a CP-Sil 88 for FAME, 100m (L) x 0.25mm (ID) x 0.25 μ m (film thickness) (Agilent Technologies, Inc., Santa Clara, CA) with a 1m (L) x 0.53mm (ID) deactivated precolumn. Calibration curves are based on injections of methyl tridecanoate, methyl PA, and methyl HA injections. Inter-assay variability (%CV) for the measurement of PA in samples with low, medium and high concentrations (1.30, 2.99, and 6.70 mg/dL) was 2.9%, 2.6%, and 3.1%, respectively. Inter-assay variability for the measurement of HA (0.56, 1.29, 3.05 mg/dL) in the same samples is 2.6%, 4.0%, and 3.9%, respectively.

The primary outcomes for the MBT include PA and HA pharmacokinetic analyses including comparison of absorption curves, C_{max} and AUC, and percent absorption of plasma PA and HA concentrations and also the HA/PA ratio 1) between CP and the healthy reference group, and 2) with pancreatic enzyme medication exposure compared with pancreatic enzyme medication -naïve status in the CP cohort.

Utilizing the relative absorption of HA to PA, the MBT has been shown to respond to changes in fat absorption in healthy adult subjects using a lipase inhibitor and in subjects with CF and PI while on and off pancreatic enzyme therapy⁴⁹, and is also sensitive to enzyme dose titration⁵⁰.

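### PA alone and HA alone rank equally with the HA/PA ratio as primary MBT outcomes for H1 and H2, and no deciding metric is named, although PA does not depend on pancreatic lipase

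*Combined protocol and SAP*

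**What the plan says.** Section 1.5 (Relevant Literature) sets out the logic of the test. PA is "a free fatty acid that does not require pancreatic lipase for absorption", whereas triheptadecanoic acid (THA), the source of HA, is "a triglyceride that requires pancreatic lipase for hydrolysis to three heptadecanoic (HA) fatty acids". The same section computes HA/PA ratios of Cmax and AUC, molar and dose-normalised, to express HA exposure relative to PA. Section 5.2.2 credits the test's past performance to that contrast: "Utilizing the relative absorption of HA to PA, the MBT has been shown to respond to changes in fat absorption".

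Section 5.2.2 nevertheless gives the components primary status: "The primary outcomes for the MBT include PA and HA pharmacokinetic analyses including comparison of absorption curves". It goes on to Cmax, AUC and percent absorption of PA and HA, with the HA/PA ratio added to the list, for both CP versus healthy and on versus off enzyme. Table 1 likewise shows PA, HA and HA/PA together under the primary outcome.

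Section 6.3.1 (Efficacy Analysis), under H1 and H2, has "differences between CP and healthy groups assessed with unpaired t tests" and paired t tests for change within CP. It then states "Metrics to be tested will be CFA%, PA and HA", followed by Cmax and AUC, the two ratios and the HA response relative to healthy subjects, with p<0.05 as the threshold. Neither section says which metric decides, which direction of PA would support a hypothesis, or that PA serves only as a control.

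**The concern.** H1 and H2 concern reduced pancreatic function. By the plan's own account, PA absorption does not need pancreatic lipase, so a PA difference between CP and healthy subjects, or between visits, points to something else: meal intake, gastric emptying, non-pancreatic absorption, body size or a period effect. HA alone carries the lipase effect and those same influences together. Only the ratio removes a factor common to both.

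With all of these metrics primary and none decisive, a non-pancreatic shift can yield a significant primary MBT result when the ratio shows nothing. It can also mask a real deficit when HA is read alone. If the metrics disagree, the plan gives the analyst no rule for which one answers the hypothesis.

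**Working it through.** **1. The plan's own MBT power (Section 6.4).** Both MBT power statements use the HA/PA ratio.
- H1: difference 0.60, SD 0.68, 22 per group. d = 0.60/0.68 = 0.882; noncentrality = 0.882 × √(22/2) = 2.93 on 42 df. Two-sided 0.05 t-test power is 81.6%. The stated 80% is reproduced.
- H2: difference 0.44, SD of differences 0.68, n = 22. d = 0.44/0.68 = 0.647; noncentrality = 0.647 × √22 = 3.03 on 21 df. Power is 82.5%. The stated 80% is reproduced.

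The trial is therefore already sized on the metric that would be made decisive.

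**2. Why a common factor matters.** Suppose a non-pancreatic influence multiplies both PA and HA in CP by f. Then PA becomes f·PA, HA becomes f·HA, and HA/PA = (f·HA)/(f·PA) is unchanged.

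**3. Illustration, false signal.** Assumptions: no pancreatic defect; log-scale two-sample t test, two-sided 0.05, 22 per group; σ = √ln(1+CV²); d = |ln f|/σ. No between-subject CV for CP is given. I start from the 45.3% (PA) and 31.9% (HA) in Section 6.4, which are between-observation figures from cystic fibrosis, and extend to 70% for both.

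| f = 0.8 | σ | d | Significant |
|---|---|---|---|
| PA, CV 45.3% | 0.432 | 0.223/0.432 = 0.52 | 39% |
| PA, CV 70% | 0.632 | 0.223/0.632 = 0.35 | 21% |
| HA, CV 31.9% | 0.311 | 0.223/0.311 = 0.72 | 64% |
| HA, CV 70% | 0.632 | 0.35 | 21% |
| HA/PA | any | 0 | 5% |

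With f = 0.7 the ranges are 45–76% for PA and 45–96% for HA; HA/PA stays at 5%.

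**4. Illustration, hidden signal.** Assume a true HA/PA of 1.02/1.62 = 0.63 of healthy (the planned Cmax contrast) and a common factor of 1.3 raising both acids in CP. HA alone is then seen at 0.63 × 1.3 = 0.82 of healthy. Power on HA alone falls from 99.8% to 55% (CV 31.9%) or from 66% to 18% (CV 70%). The ratio contrast is unaffected.

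**5. Chance movement of PA between visits.** If 45.3% is taken as the within-subject CV, the SE of the mean log Visit 2/Visit 1 ratio is 0.432 × √2/√22 = 0.130. With no true change, 95% of observed PA ratios lie within exp(±1.96 × 0.130), or 0.77 to 1.29. PA can move noticeably by chance alone.

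**The case against.** The strongest reply is that the right metric is already there. HA/PA is computed per subject with a confidence interval, PA already acts as a control in its denominator, and both power statements use the ratio. Showing the components is useful, because a ratio cannot reveal which part moved. Section 6.4 also cites earlier experience with HA alone. All of this stands, and it is why the remedy is a ranking of metrics and not a new analysis.

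A second reply is that the sentence beginning "Metrics to be tested will be CFA%, PA and HA" follows the mixed-model sentence and may list only that model's metrics. That reading is possible. The point survives it, because Section 5.2.2 separately makes PA and HA alone primary for both comparisons and Section 6.3.1 applies t tests to the MBT outcomes. The mixed model, which includes BMI, addresses change within CP and does not adjust the H1 contrast. The joint population PK model is offered only as an alternative.

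Four stronger readings are tempting and unsupported:
- *That the investigators will report a PA difference as pancreatic malabsorption.* No text says so, and H1 refers to a reduced pattern across the MBT and both stool methods. The gap is that nothing rules it out.
- *That CP subjects will be lighter and so show higher concentrations.* The dose is fixed, "with 5.0g of PA and 5.5g of THA blended into a test meal", and "history of unintentional weight loss" is one way into the CP cohort. But it is one of several and/or routes and a history item. The healthy BMI range runs from 14 to 35, and no document figure links weight to concentration. Body size is a possible source of a common shift, mainly for H1; in H2 it largely cancels within subject.
- *That a PA rise at Visit 2 shows the HA rise is not an enzyme effect.* HA may rise by more than PA, which is what the ratio detects. Given the chance range in step 5, a rule withholding attribution whenever PA moves could veto a real effect.
- *That HA itself is expected to fall by 37%.* That figure is the planned fall in the Cmax HA/PA ratio.

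**Conclusion.** The point holds as a gap in the ranking of outcomes. Stand-alone PA and HA have the same primary standing as HA/PA for H1 and H2, with no rule for which decides, although the plan's own account of the test makes the ratio the interpretable quantity. The 21–39% for PA rests on an assumed 20% common reduction and assumed CVs; neither is known for CP, and the figures illustrate sensitivity and do not forecast the result. That the ratio is untouched by a common factor is algebra and needs no such assumption. The change is worth making before analysis because it aligns the tests with the sample-size basis at no loss of power.

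**What to change.** In Sections 5.2.2 and 6.3.1 (Efficacy Analysis):
- Name the molar, dose-normalised HA/PA ratio as the MBT metric that decides H1 and H2, and state whether AUC or Cmax is primary.
- Report PA Cmax and AUC as prespecified control outcomes, giving CP/healthy and Visit 2/Visit 1 ratios with 95% CIs. State that they cannot by themselves support H1 or H2.
- Keep HA alone and the HA response relative to healthy as supportive, with a body-weight-adjusted version for CP versus healthy. Weight is already measured.
- State that if PA also shifts between visits, the enzyme conclusion rests on the change in HA/PA, with no veto based on PA.

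The cost is protocol and SAP wording only: no new data, visits or subjects. With 22 evaluable (per group for H1), power stays at 81.6% for H1 and 82.5% for H2. The downside is that a significant result on PA or HA alone can no longer be claimed as a positive primary finding.
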